11.2 Sample Size – 140 Participants

11.3 Total number of subjects requested (including records and specimens) – 140

11.4 If you are recruiting by study arm, please identify the arms of the study and how many subjects will be enrolled in each arm –

This research project will involve two study arms. Arm 1 participants will receive the SAET intervention. Arm 2 participants will receive the SCG intervention. There will be 70 subjects enrolled in each of the two arms.

11.5 Please provide a justification for your sample size

With 140 participants, 70 in each intervention arm, we will be able to potentially detect a significant difference in change in neurobehavioral symptoms between the two physical activity interventions (i.e., SAET and SCG) with an 85% power using a two-tailed test and an alpha of 0.05. This estimate is based on similar research on a civilian population (Kaplan, Vasterling, & Vedak, 2010), and takes into consideration a 20% attrition. The 140 participants recruited will suffice to address the research question for secondary aims given the same parameters.

11.6 Data Analysis Plan Complete description: Background, Objectives, Design, Step by Step how the project is going to be done

Primary Aim: Neurobehavioral symptoms: Primary analyses will evaluate whether change in neurobehavioral symptoms from pre- to immediate post-treatment, as well as from immediate post-treatment to 3 months post-treatment, differ between the physical activity interventions. In addition to assessing change in symptoms continuously, we will also evaluate reaching a clinically-relevant change in neurobehavioral symptoms (defined as a change in NSI score of 8 points) (Belanger et al., 2016). Secondary analyses will investigate differences in overall change in neurobehavioral symptoms from pre-treatment to 3 months post-treatment between the interventions using multilevel mixed-effect modeling. This approach will take into consideration between-subject variance based on randomized group, as well as within-subject variance for repeated measures. Analyses will be based on intention to treat (ITT).

Sub-Aim 1: Cognitive Performance: Similar statistical approach as Aim 1 will be conducted for Sub-Aim 1. Exposure will remain as the type of intervention (i.e. SAET vs. SCG); however, outcome will be on global deficit score based on the cognitive test scores.

Sub-Aim 2: Physiological Adaptation: Analysis of Variance (ANOVA) will be utilized to determine differences in continuous variables of physiological adaptation (i.e., cerebrovascular flow, improved cardiovascular health) between interventions.

Sub-Aim 3: Warfighter Performance: ANOVA will be utilized to determine differences in M-ADL scores between interventions. As described in Table 3, participants will be categorized as passing or not passing their CFTs. As such, given >10% with passing CFTs, we will utilize Poisson regression with robust error variable to determine the prevalence ratio of passing CFTs between the physical activity interventions.

A significant p-value of 0.05 will be used to assess main effects.

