9.3 Objectives/Specific Aims/Research Questions

Describe the purpose and objective(s) of the study, specific aims, and/or research question/hypotheses

1. Objective

Past research demonstrates that SAET is a safe and effective treatment to improve neurobehavioral symptoms and return patients to pre-injury activities following concussion. However, this work has almost exclusively involved civilian populations with sport-related concussion. Its translation to military mTBI has yet to be examined. Mechanism of injury (e.g., blast vs blunt), time since injury, and co-morbid psychological trauma differs notably in the military-related brain injuries compared with sport-related brain injury.

Incorporating personalized exercise into the management of mTBI in a military population is advantageous on multiple levels. It is believed to improve treatment efficacy on physiological, cognitive, and psychological parameters and may also facilitate the integration of injured warfighters back to their units at full readiness (a primary objective of military medicine) by improving locomotion and mitigating deconditioning during convalescence.

The objective of this study is to develop a prescribed exercise treatment program for warfighters with mTBI that can be personalized for SM needs (i.e., medical and occupational) and is adaptable to variable clinical resources (e.g., forward operating bases, rural clinics, and mTBI specialty programs). This clinical trial is proposed to evaluate the efficacy of an exercise treatment for MTBI as determined primarily by symptom resolution, improved mental health, enhanced physiological functioning/locomotion, as well as RTD.

2. Specific Aims/Hypotheses:

The study will be a randomized clinical trial among active duty service members (SMs) with persistent cognitive complaints following mTBI, comparing a prescribed sub-symptomatic adaptable exercise treatment (SAET) to an active stretching control group (SCG). SAET's overall effectiveness will be assessed by neurobehavioral symptom resolution. Additional exploratory aims will include cognitive performance, physiological adaptation and locomotion as well as functional changes in military performance. These items will be addressed in the following aims:

Primary Aim:

To determine whether SAET is more effective than the control condition in reducing neurobehavioral symptoms among SMs with persistent complaints following mTBI.

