Hypothesis 1: There will be a greater reduction in the Neurobehavioral Symptoms Inventory (NSI) from pre- to post-SAET compared to the control condition. A similar finding will continue from immediate to 3 month post-SAET.

Secondary Aims:

Sub-aim 1 Cognitive Status: To determine if SAET is effective at improving cognitive impairment among SMs with persistent complaints from mTBI.

Sub-hypothesis 1: There will be a greater decrease in the Global Deficit Scores (GDS; an overall measure of cognitive impairment) post SAET in comparison to the control condition.

Sub-aim 2 Physiological Adaptation: To measure physiological adaptation associated with SAET compared to the control condition.

Sub-hypothesis 2: SAET will be associated with improved cerebrovascular blood flow regulation, as measured by Transcranial Doppler and improved cardiovascular function, as measured by changes in heart rate variability (HRV) and estimated maximal oxygen consumption (est. VO₂ max) compared to the control condition.

Sub-aim 3 Warfighter Performance: To determine if SAET participants will have improved locomotion and a higher level of occupational performance compared to the control condition.

Sub-hypothesis 3: SAET participants will have improved locomotion and physical performance (based on the Marine Corps Combat Fitness Test(CFT)) and higher ratings of occupational performance (based on supervisor ratings on the Checklist of Military Activities of Daily Living [M-ADL]) after completion of treatment and 3 months post-treatment compared to the control condition.

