The second 20 minutes of each exercise session will be composed of a series of 5 predetermined exercises that rotate every day. Each workout will have one or two alternatives that the patient can complete either for modification to accommodate a physical limitation or to optimize preference. Resistance training each day will include multi-joint functional movements along with stability work. Exercise programs completed in the clinical space will be supervised by a Physical Therapist or Exercise Physiologist and HR will be recorded. For independent (home-based) exercise days, the patient will be prompted to use the wearable device and to complete the ECQ. The exercises will include the use of standard fitness equipment. All participants will have access to the clinic fitness center as well as military fitness centers for independent work out sessions. If needed, participants will also be given resistance exercises that can be completed at home without equipment. The last five minutes of the session will include more mobility work, and/or cooling down.

Participants randomized to the SCG control group will complete a total of 40 hours of stretching exercises. SCG will be led by an Exercise Physiologist or Physical Therapist and stretching exercises will be completed in the clinic two days per week and independently outside of the clinic 3 days per week for 8 weeks. Total duration will be for 8 weeks. Stretching exercises are designed not to increase heart rate or have excessive head motion. (**Figure 3**).

All participants will have their physical activity measures recorded using a wearable sensor, ECQ and EHQ:

Wearable sensor: Participants will use a consumer based wearable sensor that is designed to track health information during daily activities. Measurements may include heart rate, heart rate variability (HRV), respiration, body temperature, sleep data and movement. This device will be paired with app that will allow users to view their data in real time. Such devices have been used in DoD sponsored research (Altini & Kinnunen, 2021; Asgari Mehrabadi et al., 2020; Kinnunen, Rantanen, Kentta, & Koskimaki, 2020; Stone et al., 2020).

Exercise Compliance Questionnaire: To supplement wearable sensor information, participants will be instructed to record the type of exercise, date, time of exercise, duration of exercise, perceived exertion rating, self-reported symptoms and/or other data points that will gauge compliance and engagement.

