If you experience an increase in your current symptoms (by 2 points on a 0-10 scale) or onset of two new symptoms of concussion while exercising at home and cannot continue, please stop for that day and try again the following day. If you experience a prolonged or severe increase of your concussion-related symptoms during exercise, then do not perform the prescribed exercises and contact your doctor.

Example Day 1 Prescribed Exercise Program

REMINDER: Note your target heart rate (page 1), wear your heart rate monitoring device, and stop exercising if your symptoms worsen.

Day 1: With Trainer

- 1: 5 Minutes Warm Up
- 2: Minimum 20 minutes at target heart rate
- 3: Minimum 20 minutes resistance training (see below)
4. 5 Minute Cool Down

Resistance Work-Out and Medications Day 1

Exercise 1: Sit Ups: 20 standard sit-ups, 3-5 sets

Modifications: 30 second plank or 20 crunches

Exercise 2: Standard Bench Press, 3-5 sets with 10 repetitions

Modifications: dumbbell chest press or push ups

Exercise 3: Dumbbell Shoulder Press, 3-5 sets with 10-12 repetitions

[figure not shown]
Modifications: Banded shoulder press or machine shoulder press

Exercise 4: Incline Dumbbell Fly, 3-5 sets with 10-12 repetitions

Modifications: incline chest press or decline push up

Exercise 5: Triceps Pushdown, 3-5 sets with 10-12 repetitions

Modifications: Triceps Dip, Bent Over Triceps Extension

Figure 3. Example SCG Program

YOUR PERSONAL STRETCHING PRESCRIPTION

Your doctor has given you a prescription for light stretching. For this research study, it is important that you follow the instructions given by your doctor below very carefully!

You will do stretching exercises each day, without doing any other type of exercise that gets your heart rate up. Your doctor has decided on a stretching routine that is safe for you, and that should not cause you to

have any concussion symptoms. If your doctor appointment is during Days 1-6 of a stretching cycle, do not do the stretches for that day. The day after your appointment, resume doing stretches.

You will be asked to tell us how you are feeling and your activity level.

Please wear your heart rate monitoring device during the exercise.

HERE IS THE PRESCRIPTION THAT YOU MUST FOLLOW

Please see the attached sheet for instructions/demonstrations of stretches that you should do each day/week. They change each day, so be sure to follow the booklet as written.

[figure not shown]
Example Day 1 Prescribed Stretching Program

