11.0 Statistical/Data Analysis Plan

11.1 Statistical Considerations:

List the statistical methods to be used to address the primary and secondary objectives, specific aims, and/or research hypotheses. Explain how missing data and outliers will be handled in the analysis. The analysis plan should be consistent with the study objectives. Include any sub-group analyses (e.g., gender or age group). Specify statistical methods and variables for each analysis. Describe how confounding variables will be controlled in the data analysis

1. Data Analyses

The difference between treatment groups sample characteristics including demography, military information and co-variates will be evaluated using Student's 't' and chi-square tests for continuous and categorical variables, respectively. Wilcoxon Rank-Sum test will be used for two-group comparisons where continuous variables are non-normally distributed. We will leverage the statistical power of multilevel modeling to handle missing follow-up data.

Please see section 11.6 for the data analysis plan.

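### The primary NSI follow-up contrast (post-treatment to 3 months) supports SAET only if the gap widens after treatment ends; if Hypothesis 1 means a persisting advantage, no primary contrast tests it

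*Protocol*

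**What the plan says.** The Primary Aim in section 9.3 is "To determine whether SAET is more effective than the control condition in reducing neurobehavioral symptoms". Hypothesis 1 predicts a larger fall in NSI with SAET than with control from before to after treatment, and then adds: "A similar finding will continue from immediate to 3 month post-SAET".

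Section 11.6 turns this into two primary between-arm comparisons, asking whether NSI changes "from pre- to immediate post-treatment, as well as from immediate post-treatment to 3 months post-treatment, differ between the physical activity interventions". The overall change is placed one rank lower: "Secondary analyses will investigate differences in overall change in neurobehavioral symptoms from pre-treatment to 3 months post-treatment", analysed with a mixed-effects model. The analysis is by intention to treat, and section 11.1 adds "We will leverage the statistical power of multilevel modeling to handle missing follow-up data".

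Both programmes run for 8 weeks (section 10.1; for the control arm, "Total duration will be for 8 weeks"). No equivalence or non-inferiority margin is given for the post-treatment interval. Section 11.5 states 85% power, a two-sided 0.05 test, 70 per arm and 20% attrition. It gives no effect size, SD or correlation and does not say which change was powered.

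**The concern.** The word used in Hypothesis 1 for the follow-up period leaves two readings open. One is that SAET participants go on improving more than controls after treatment stops. The other is that the advantage reached at the end of treatment is still there at 3 months. These need different contrasts, and the plan gives primary rank only to the one that fits the first.

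If persistence is meant, a fully kept benefit would leave the follow-up half of Hypothesis 1 unsupported on its primary contrast. A partial fade could be reported as a significant primary result favouring control at a time when SAET is still ahead. What is at stake is which contrast carries the 3-month claim. The pre-to-post test is not affected, and no information is lost, because the pre-to-3-month analysis is already planned.

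**Working it through.** **Part that needs no assumption.** Let G0, G1 and G2 be the mean SAET advantage on the NSI at pre-treatment, immediate post-treatment and 3 months. Randomisation makes the expected G0 zero.

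- Pre-to-post contrast: A = G1 − G0
- Post-to-3-month contrast: B = G2 − G1
- Pre-to-3-month contrast: C = G2 − G0 = A + B

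Write G2 = k·G1, with G1 > 0. Then B = (k − 1)·G1 and C = k·G1. B is zero at k = 1, negative (favouring control) for 0 < k < 1 although C is still positive, and positive only for k > 1. This holds for any sample size, SD or correlation.

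**The plan's own figure.** The total of 140 cannot be reproduced, because no effect size is given. The attrition step is consistent: 70 × 0.80 = 56 completers per arm. With 56 per arm, two-sided 0.05 and 85% power, the noncentral t distribution gives a standardised difference in change of d = 0.571.

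**Illustrative power.** Assumptions: the 85% belongs to the pre-to-post contrast; SD is 1 at each visit; correlations are either equal between all visits, or falling (pre-post 0.6, post-3-month 0.7, pre-3-month 0.5).

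- Gap at post-treatment: D = d·√(2 − 2r_pre,post). In the falling case, 0.571 × √0.8 = 0.511.
- Standardised effect for B: (k − 1)·D/√(2 − 2r_post,3m)
- Standardised effect for C: k·D/√(2 − 2r_pre,3m)

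Ranges run across the two correlation patterns.

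| Share of gap left at 3 months | Post-to-3-month, significant for SAET | Post-to-3-month, significant against SAET | Pre-to-3-month, significant for SAET |
|---|---|---|---|
| All (k = 1) | 2.5% | 2.5% | 76-85% |
| Three quarters (k = 0.75) | 0.2-0.3% | 11-14% | 52-61% |
| Half (k = 0.5) | under 0.1% | 32-41% | 27-32% |

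The post-to-3-month contrast reaches 85% power only when the gap grows to 1.87-2.0 times its post-treatment size. Example for the falling case: (k − 1) × 0.511/0.775 = 0.571 gives k = 1.87.

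**Interval widths.** The 95% half-width is 1.98 × √(2/56) = 0.375 SD of the change score.

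- Post-to-3-month, equal correlation: 0.375/0.571 = 66% of the gap. Falling: 0.375 × 0.775/0.511 = 57%.
- Pre-to-3-month, equal correlation: 66%. Falling: 0.375 × 1/0.511 = 73%.

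A post-to-3-month estimate centred on zero therefore cannot exclude loss of half the benefit.

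**Sensitivity.** A likelihood mixed model on 70 per arm with 20% attrition gives, for a kept benefit, 2.5% on post-to-3-month and 79-87% on pre-to-3-month. With a quarter lost it gives 11-14% against SAET and 54-64% for it. Varying d from 0.4 to 0.7, a kept benefit gives 2.5% against 47-96%, and a quarter lost gives 8-18% against SAET on post-to-3-month.

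**The case against.** The strongest reply is that the plan is consistent as written. Hypothesis 1 and section 11.6 name the same two intervals in the same order, and a similar greater reduction over the second interval is exactly what the second contrast tests. Where the authors mean status at a visit, as in Sub-hypothesis 3, they name the visits. Section 9.2 also offers reasons to expect later gains: earlier work on activity in later months after injury, autonomic recalibration and neuroplasticity. This stands. A reader might infer that the protocol contradicts itself or that the contrast is simply wrong; the documents do not support that. The fault is conditional on persistence being meant.

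A second reply is that the pre-to-3-month contrast does not prove that benefit is kept either. This also stands. A significant result shows only that some benefit is present. Its interval is 66-73% of the gap, no narrower than the 57-66% criticised above, and it is still significant in 27-32% of trials when half the benefit has gone.

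Third, fixed-order testing is not plainly better. If the effect emerges late, with d = 0.3 at post-treatment (an assumption), the pre-to-post gate passes only about 35% of the time with 56 per arm and would block a 3-month claim. This stands, so a fixed order is an option only.

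A reader might also infer that the gap must narrow after week 8, since the example control sheet tells participants to stretch "without doing any other type of exercise that gets your heart rate up" and the protocol states no activity rule after treatment. That is plausible, but it is an inference and the conclusion does not need it.

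Deferring the matter to the SAP does not answer it, because the protocol itself assigns the primary and secondary ranks.

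**Conclusion.** The point holds in a limited form. The primary follow-up contrast can support SAET only through further separation after treatment ends, and the protocol does not say clearly whether that or persistence is meant. If persistence is meant, no primary contrast tests it, and a null post-to-3-month result cannot stand in for it without a margin.

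The sign argument is exact. The percentages are illustrations resting on a back-solved effect, assumed correlations and the assumption that the stated power refers to pre-to-post change. Re-ranking is worthwhile on either reading of the wording, because the Primary Aim, whether SAET reduces symptoms more than control, is answered at 3 months by change from the randomised baseline. It should be fixed, but it does not threaten the trial: the end-of-treatment test is sound and every contrast is already planned.

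For the cognitive score, section 11.6 says "Similar statistical approach as Aim 1 will be conducted for Sub-Aim 1", so the same ranking carries over. Sub-hypothesis 1 makes no explicit 3-month claim, so the point matters there only if one is made.

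**What to change.** - Keep the between-arm difference in NSI change from pre- to immediate post-treatment as the primary test.
- Make the already planned pre-to-3-month between-arm difference the contrast for the 3-month claim. Describe it as showing that a benefit is still present at 3 months, not that it is fully kept.
- Report post-to-3-month change as supportive, with a confidence interval.
- Reword the second half of Hypothesis 1 so that it states a between-arm difference in change from pre-treatment at 3 months.
- If further gain after treatment is really meant, say so, and state that a null post-to-3-month result is not read as loss of benefit.
- Use the same ranking for the cognitive score if a 3-month claim is made for it.

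Testing the two NSI contrasts in fixed order is one way to control error, but it is not a required part of the change.

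Cost: a change of rank and wording, with no new data or analyses. The downside is that post-to-3-month change is no longer primary.

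### Section 11.6 makes two NSI contrasts primary, and leaves an 8-point responder analysis unplaced, without saying which result decides the primary aim at the single alpha of 0.05

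*Protocol*

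**What the plan says.** The Primary Aim paragraph of Section 11.6 introduces its primary analyses in the plural. The first is the between-arm comparison of NSI change from pre-treatment to immediate post-treatment. The second is joined to it on equal terms: whether changes "as well as from immediate post-treatment to 3 months post-treatment, differ between the physical activity interventions". The next sentence adds a second scale: "In addition to assessing change in symptoms continuously, we will also evaluate reaching a clinically-relevant change in neurobehavioral symptoms", defined as 8 NSI points. Only after that does the paragraph turn to secondary analyses, namely overall change from pre-treatment to 3 months in a mixed model.

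Section 11.6 closes with its only significance rule: "A significant p-value of 0.05 will be used to assess main effects".

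Section 11.5 claims power to "detect a significant difference in change in neurobehavioral symptoms between the two physical activity interventions" "with an 85% power using a two-tailed test and an alpha of 0.05". It names neither an interval nor a scale.

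Hypothesis 1 in Section 9.3 predicts a greater NSI reduction with the exercise treatment from pre- to post-treatment, and then a similar finding from immediate post-treatment to 3 months. It gives no rule for combining the two parts.

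**The concern.** A two-sided alpha of 0.05 is a promise about one decision. Section 11.6 offers at least two results that could each be presented as the primary one, and the protocol does not say how they combine. A reader of the final report could not tell whether success was meant to rest on the first contrast, on either, or on both.

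The two contrasts also share the immediate post-treatment visit, so chance error at that visit pushes them in opposite directions. One could favour exercise while the other favours stretching, and the protocol does not say how that would be read. The stakes are the error rate behind the trial's main claim and the freedom to choose the deciding result once the data are known.

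**Working it through.** **1. The plan's own figure.** Section 11.5 gives "With 140 participants, 70 in each intervention arm", and says that the estimate "takes into consideration a 20% attrition". That leaves 70 × 0.8 = 56 evaluable per arm. No effect size or SD is stated; the text says only "This estimate is based on similar research on a civilian population". The 85% can therefore be neither confirmed nor refuted. Solving backwards, the standardised difference detectable with 85% power at two-sided 0.05 is

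d = (1.960 + 1.036) × √(2/56) = 0.566 (0.571 with the t distribution).

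This is one comparison at one alpha. The text does not show which comparison it is.

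**2. If the tests were independent.** The chance of at least one false positive in k tests, each at 0.05, is 1 − 0.95^k:

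- k = 2: 9.75%
- k = 3: 14.3%
- k = 4: 18.5%

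These overstate the problem, because the tests are correlated.

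**3. Correlation of the two primary contrasts.** Take equal variance at each visit and equal correlation ρ between visits. In units of the visit variance, the two successive changes have covariance −(1 − ρ), and each has variance 2(1 − ρ). Their correlation is −0.5 whatever the SD and ρ.

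**4. Simulation with no treatment effect.** 56 per arm, 20,000 trials per setting. Assumed, not from the protocol: NSI means 35, 30 and 28 in both arms, SD 12 or 16, equal visit correlation 0.5 to 0.9. Continuous changes were compared by t-test, and drops of at least 8 points by a pooled two-proportion test, each at 0.05.

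| Tests that may be claimed | Chance of at least one p < 0.05 |
|---|---|
| Two continuous contrasts | 8.7% to 9.4% |
| Plus the responder test on one interval | 11.3% to 12.1% |
| Plus responder tests on both intervals | 14.1% to 15.1% |
| Both continuous contrasts required | 0.8% to 1.0% |

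The first and last rows agree with each other: 5% + 5% − about 0.9% ≈ 9.1%. The simulation standard error near 9% is √(0.09 × 0.91/20,000) = 0.2 percentage points, so much of the spread in the first row is noise. Further runs with SD 15 and equal or autoregressive correlations of 0.5 to 0.85 gave 8.7% to 9.9% for the two continuous contrasts and 13.9% to 15.3% for all four tests.

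**5. Comparing remedies.** At the back-solved d = 0.566 with 56 per arm, a fixed sequence leaves the first test at 0.05 and 85% power. Splitting alpha equally over two tests (0.025 each) gives 77.5%. Restoring 85% would then need 68 evaluable per arm, or 68/0.8 = 85 enrolled per arm and 170 in total.

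**The case against.** The strongest defence is Hypothesis 1. It puts the pre-to-post reduction first and presents the follow-up result as its continuation, within one hypothesis. Read as requiring both, it would hold alpha comfortably, at about 1%. That reading is possible, but neither Section 9.3 nor Section 11.6 states it, and the 85% power would then not describe the joint requirement. The either-may-win rule is not stated either, so the 9% is conditional on it.

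A reader might infer that the primary aim is tested four ways, each at 0.05, so that the error rate is about three times nominal. The protocol does not support this. It neither calls the responder analysis primary nor says it is run on both intervals, and reading it as supportive is at least as natural. The closing rule speaks of main effects and does not expressly cover the responder analysis. The 14% to 15% is therefore the widest reading.

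A reader might also infer that the trial is underpowered because correction would cost power. The protocol proposes no such correction, and none is needed with a single named test.

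Finally, testing order is often left to a statistical analysis plan, and one may exist. Its absence from the protocol is not the complaint. The complaint is what the protocol does fix: two contrasts on equal primary footing against a single stated alpha. A later plan would have to override that text.

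**Conclusion.** The point holds in a limited form. If success on either contrast labelled primary may be claimed, the false-positive chance is about 9% against the stated 5%. Counting one responder test brings it to about 11% to 12%, and counting two to about 14% to 15%. The inflation appears under each of these counts, so the conclusion does not depend on how the responder sentence is read. It does depend on no both-must-succeed rule being in force.

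The figures rest on 56 completers per arm and on assumed NSI means, SDs and visit correlations. Under equal visit correlations the two-contrast figure is insensitive to the assumed SD and correlation. This should be corrected before analysis. It is an ambiguity about the deciding test and does not undermine the design or the sample size. Whether the 85% power belongs to the first contrast cannot be settled from the protocol.

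**What to change.** In Section 11.6, name the between-arm difference in continuous NSI change from pre-treatment to immediate post-treatment as the single primary test, at two-sided 0.05. Test the immediate post-treatment to 3 months contrast only if the first is significant. Report the 8-point responder comparisons as supportive estimates with confidence intervals, and state the interval for each.

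In Section 11.5, state which interval and scale the 85% power was calculated for. The sponsor should first check that the calculation matches the named primary test, because the section gives no interval, scale, effect size or SD.

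The cost is wording in two sections plus that check. The sequence itself changes neither the 140 participants nor any visit or procedure. The downside is that the follow-up contrast cannot be claimed if the first test fails.
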